11.5 Dose Level Guidelines

Not Applicable.

11.6 Secondary or Exploratory Elements (including correlative science aims)

Secondary Hypotheses and Endpoints:

There are no specific secondary hypotheses regarding secondary objective. The purpose of secondary objective is to describe the survival functions for progression-free survival (PFS) and overall survival (OS).

Definitions of Secondary Endpoints and How These Will Be Analyzed

Progression-free survival is defined as the duration of time from study entry to time of progression, death, or the date of last contact, whichever occurs first. PFS is censored in patients who are alive and have not progressed.

Overall survival is defined as the duration of time from study entry to time of death or the date of last contact. OS is censored in patients who are alive.

The PFS and OS survival functions will be visualized using Kaplan-Meier curves, and summarized using medians of PFS and OS as well as proportions of PFS and OS at the one-year and 3-year follow-up times.

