4.8 Subject Withdrawal/Discontinuation Criteria

Subjects may withdraw consent at any time for any reason or be dropped from the trial at the discretion of the investigator should any untoward effect occur. In addition, a subject may be withdrawn by the investigator or the Sponsor if enrollment into the trial is inappropriate, the trial plan is violated, or for administrative and/or other safety reasons.

A subject must be discontinued from the trial for any of the following reasons:

• The subject or legal representative (such as a parent or legal guardian) withdraws consent. Version 9.0, 26 April 2023

- Confirmed radiographic disease progression
- Intercurrent illness that prevents further administration of treatment
- Investigator's decision to withdraw the subject
- The subject has a confirmed positive serum pregnancy test
- Noncompliance with trial treatment or procedure requirements
- The subject is lost to follow-up
- Completed 24 months of uninterrupted treatment with pembrolizumab or 35 administrations of study medication, whichever is later.

Note: 24 months of study medication is calculated from the date of first dose. Subjects who stop pembrolizumab after 24 months may be eligible for up to one year of additional study treatment if they progress after stopping study treatment.

- Administrative reasons
- In case of radiographic complete response confirmed with 2 consecutive CAT scans 12 weeks apart, patient may be discontinued from study.

After the end of treatment, each subject will be followed for 30 days for adverse event monitoring (serious adverse events will be collected for 90 days after the end of treatment). Subjects who discontinue for reasons other than progressive disease will have post-treatment follow-up for disease status until disease progression, initiating a non-study cancer treatment, withdrawing consent or becoming lost to follow-up. After documented disease progression each subject will be followed by telephone for overall survival until death, withdrawal of consent, or the end of the study, whichever occurs first.

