Note: In order to more precisely determine time of progression, the investigator is encouraged to obtain radiologic assessments earlier than 12 weeks if there is a strong clinical suspicion of progression of disease to either confirm or refute the clinical impression.

End-of- Treatment Visit:

- Physical examination will be performed. A pelvic examination is required if this method is used to measure your disease.
 - A CT scan of the chest, abdomen and pelvis will be performed, if not done within prior 12 weeks.
 - Blood test for CBC, Chemistry,

Follow-up:

Subjects will need to see their doctor every 3 months to check the status of their disease for 2 years following study treatment. Afterwards, they will see the doctor every 6 months for 3 years and then yearly.

Patients who have completed study treatment or who have discontinued study treatment for reasons other than Progressive Disease per RECIST 1.1 will continue to be evaluated with tumor assessments every 12 weeks (+/-14 days) until documentation of Progressive Disease, withdrawal of consent or until the patient starts subsequent anti-cancer therapy, whichever comes first.

Patients will be followed every 3 months for survival only after disease progression. This may be performed by telephone follow up.

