6.1.1.5.3 Subsequent Anti-Cancer Therapy Status

The investigator or qualified designee will review all new anti-neoplastic therapy initiated after the last dose of trial treatment. If a subject initiates a new anti-cancer therapy within 30 days after the last dose of trial treatment, the 30 day Safety Follow-up visit must occur before the first dose of the new therapy. Once new anti-cancer therapy has been initiated the subject will move into survival follow-up.

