7.0 EVALUATION CRITERIA

7.1 Objective Response

The major parameters of response to be assessed include complete and partial responses, Progression-Free Survival, Overall Survival, documentation of Sites of Recurrence, and Treatment Related Toxicity. Treatment response will be based on RECIST v1.1 Guidelines for Measurable Lesions.

Measurable Lesions- Only recurrent patients with measurable lesions will be enrolled in the study. All target lesions must be assessed using the same technique as baseline. Included in the evaluations are the following standard response criteria for target lesions:

- Complete Response (CR): Disappearance of all target lesions. No new lesions. Lymph nodes must be <10mm short axis.
- Partial Response (PR): At least a 30% decrease in the sum of the longest diameter of target lesions, taking as reference the baseline sum of the longest diameters. No new lesions.
- Progressive Disease (PD): The appearance of a new lesion, or at least a 20% increase in the sum of the longest diameters of the target lesions, taking as the reference the smallest sum of the longest diameters recorded since treatment started, and at least 5mm increase.
- Stable Disease (SD): Target lesions do not qualify for CR, PR, or progression. No new lesions.

All non-target lesions must be assessed using the same technique as baseline. Included in the evaluations are the following standard response criteria for non-target lesions:

- Complete Response: The disappearance of all non-target lesions.
- Incomplete Response/Stable Disease: The persistence of one or more non-target lesion(s).
- Progression Disease: The appearance of one or more new lesions and/or unequivocal progression of existing non-target lesions.

Objective Response (OR) will be defined as Complete or Partial Response using CR or PR as described by the above RECIST v1.1 Response Criteria.

Progression-Free Survival (PFS) will be defined as date from entry to a particular protocol to date of reappearance or increasing parameters of disease on imaging (CT scan or MRI) or by clinical exam or death from any cause, or is censored at date of last disease assessment.

Overall Survival (OS) will be defined as observed length of life from entry to a particular protocol to death or, for living patients, date of last contact.

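### PFS is censored at last disease assessment in section 7.1 but at last contact in section 11.6, so under 11.6 time without scheduled assessment can count as progression-free

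*Combined protocol and SAP*

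**What the plan says.** **The two definitions.** Section 7.1 runs PFS from entry to worsening or returning disease "on imaging (CT scan or MRI) or by clinical exam", or to death from any cause, and otherwise censors at the "date of last disease assessment". For OS it uses, "for living patients, date of last contact". Section 11.6 defines PFS as "the duration of time from study entry to time of progression, death, or the date of last contact, whichever occurs first" and censors patients who are alive and unprogressed. Its OS definition uses the same last-contact date. Section 11.6 then names the PFS summaries: Kaplan-Meier curve, median, and one- and three-year proportions.

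**Follow-up after stopping treatment without progression.** Section 4.8 provides "post-treatment follow-up for disease status until disease progression, initiating a non-study cancer treatment" or two other stopping points. The Follow-up text of section 6.1 continues 12-weekly tumour assessments until progression, "withdrawal of consent or until the patient starts subsequent anti-cancer therapy, whichever comes first". Section 6.1.1.12 also lists new anticancer treatment among the points where imaging ends. Section 6.1.1.5.3 adds: "Once new anti-cancer therapy has been initiated the subject will move into survival follow-up".

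**Text pointing the other way.** Section 6.1.1.11 says in general terms that imaging goes on until progression and does not mention new therapy. The Follow-up text also has patients see their doctor every three months to "check the status of their disease for 2 years following study treatment", and less often after that.

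Neither PFS definition says what happens when new anticancer therapy starts.

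**The concern.** The plan holds two PFS rules and no order of precedence. For most patients they agree or nearly agree. They part for a patient who stops treatment unprogressed, starts another anticancer therapy and stays in contact for survival. Scheduled assessment has ended, yet under 11.6 the patient remains at risk and progression-free until death, last contact or an incidentally recorded progression.

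At stake are the PFS median, the one- and three-year proportions, and the exploratory Cox models for PFS in section 11.7. The trial is open-label, so an unresolved choice could also be settled after the data are seen.

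**Working it through.** **1. The plan's own figures.** The only design calculation concerns response (section 11.3, Table 8). With b the binomial probability, the chance of stopping early is Σ b(x; n1, p) over x ≤ r1. The chance of declaring the regimen interesting is Σ b(x; n1, p) × P[Bin(n − n1, p) ≥ r + 1 − x] over x > r1. Here r1 = 0 for n1 = 8–13 and 1 for 14–15; r = 1 for n = 18 and 2 for 19–25. Averaging over the 8 × 8 = 64 equally weighted accrual pairs gives:

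| Quantity | Stated | Recomputed |
|---|---|---|
| Power at 25% | 90.0% | 90.05% |
| Alpha at 5% | 9.5% | 9.45% |
| Early termination at 5% | 64.9% | 64.89% |
| Expected N at 5% | 15.14 | 15.13 |

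The figures reproduce, and none uses PFS.

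**2. Who is affected.**
- Progression recorded: same event date under both rules.
- Death without recorded progression: same event date under both.
- Alive, unprogressed, still being scanned: the censoring dates differ by about one scan interval.
- Alive, unprogressed, on new therapy: 7.1 censors at the last assessment, 11.6 at last contact, possibly years later.

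The last group drives the gap.

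**3. Simulation of the one-year gap.** From the documents: scans at weeks 6 and 12 and every 12 weeks; 36 months' accrual; two cut-offs. Month 48 is 1 July 2016 to the estimated end on 30 June 2020. Month 82 is 1 July 2016 to the version date of 26 April 2023 (81 months and 25 days). Assumed: exponential progression with a 9-month median; median post-progression survival 24 months; 5%, 10% or 20% assigned to switch in months 1–9, of whom enough are still unprogressed that about 4%, 7.5% or 15% of all patients switch; later progressions recorded at three-monthly visits with probability 0, 0.5 or 1. Each scenario has 400,000 patients. Under 11.6, living unprogressed patients are censored at cut-off. Under 7.1, they are censored at the last scan before switch or cut-off. Deaths are events under both.

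One-year PFS, 11.6 minus 7.1, in points, for 4% / 7.5% / 15% switching:

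| Later progressions recorded | Month 82 | Month 48 |
|---|---|---|
| None | +0.4 / +0.9 / +1.6 | +1.1 / +2.1 / +4.2 |
| Half | +0.2 / +0.5 / +0.9 | +0.7 / +1.4 / +2.9 |
| All | 0.0 / +0.1 / +0.1 | +0.3 / +0.7 / +1.4 |

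The gap shrinks with longer follow-up because more switchers have died, and a death is dated the same way under both rules.

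**4. Visits treated as assessments.** The table lets a visit record an event but not serve as a last disease assessment. If a visit does both, the all-recorded gap is 0.1 point or less. The half-recorded gap then lies between about 0 and 2.2 points, depending on how partial capture is modelled.

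**5. Other time points and medians.** At month 82 the three-year gaps are +1.0 / +1.9 / +3.6 (none recorded) and 0.0 / +0.1 / +0.2 (all recorded). At month 48 only 0.4 to 1.2 of 25 patients would be at risk at 36 months, so that gap carries little information. A separate simulation used median PFS of 6, 12 and 24 months, 36–60 months of follow-up, 4% to 24% switching and nothing recorded afterwards. Its one-year gaps run from 28.5 − 28.1 = 0.4 to 55.3 − 53.8 = 1.5 points, and its three-year gaps from 3.8 − 2.6 = 1.2 to 44.4 − 36.8 = 7.6 points. The estimated median moved only in the 24-month case, from 25.1 months under 7.1 to 27.8–30.6 under 11.6.

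**6. Sampling error.** With one-year PFS of 42.8% (no switching) and 25 patients, SE = √(0.428 × 0.572 / 25) = 0.099, about 10 points.

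**7. What the date change leaves.** At month 82, 15% switching, none recorded: 48.2% under 11.6, 46.6% under 7.1, 42.8% with no switching. Changing the date removes 48.2 − 46.6 = 1.6 of an excess of 48.2 − 42.8 = 5.4 points. The other 46.6 − 42.8 = 3.8 points remain because 7.1 counts a switcher's late death as the event when the earlier progression was not seen.

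**The case against.** The best defence is that little turns on this. Treatment continues until progression or toxicity, so switching while unprogressed needs a particular route, and the documents give no rate. Section 6.1.1.11 and the three-monthly visits suggest later progressions may be found, and 7.1 accepts clinical examination. PFS has no hypothesis, and the gap is well inside sampling error. All of that stands as to size. It does not reconcile the two dates. Sections 4.8, 6.1 and 6.1.1.12 deal specifically with patients off treatment and end scheduled assessment at new therapy.

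Three stronger readings are tempting but unsupported:
- **The sections contradict each other on what counts as progression.** Section 11.6 only uses the word; 7.1 defines it. A shorter statement is not a conflict.
- **Section 7.1 is right and 11.6 is inflated.** The direction is not fixed. At month 48, 15% switching, all recorded, 11.6 gives 43.1% and 7.1 gives 41.7%, against 42.8% with no switching. If switchers truly stay progression-free, censoring them early can make 7.1 too low.
- **The effect is large.** Take 25 patients event-free at week 24, three switching just afterwards, and 12 others progressing by month 12. That gives 13/25 = 52.0% against 10/22 = 45.5%. This exceeds every simulated one-year gap, and a 9-month median would have about 35% progressed by week 24.

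**Conclusion.** The conflict in censoring dates is real, is in current text and needs no assumption to establish. Its consequence follows from the follow-up rules: under 11.6, time after new therapy without scheduled assessment can count as progression-free.

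The size does rest on assumptions. Month 82 suits the version date and the five years of follow-up in section 11.4 better than month 48 does. On that footing, with 4% to 15% switching, the one-year gap is about 0.4 to 1.6 points if nothing later is recorded and about 0 if everything is. At month 48 it reaches about 4 points with nothing recorded. It is zero if nobody switches and visits are timely. Three-year gaps can be larger but depend heavily on the assumed median and follow-up.

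Severity is minor. A reader might infer that the efficacy conclusion is at risk; it is not, because the response rule, alpha, power and sample size do not involve PFS.

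**What to change.** In section 11.6, replace the last-contact date for PFS with the "date of last disease assessment", and refer to section 7.1 so that the two definitions are identical. Keep last contact for OS only.

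Separately, state in that single definition how the start of new anticancer therapy is handled. One option is to censor at the last assessment on or before it, with the alternative as a sensitivity analysis. This is the sponsor's choice of estimand. It is needed because the date change alone removes only part of the possible bias.

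The cost is a sentence or two, one optional sensitivity analysis and no new data. Reported PFS may be slightly lower than under 11.6.

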11.7 Exploratory Hypothesis and Endpoints

Dot plots and box plots in conjunction with Spearman's correlation analysis will be used to explore the associations of tumor expressions of PD-L1, PD-1, lymphocyte infiltration and other interesting biomarkers (such as CD4+,CD8+, FoxP3, CD25, LAG-3, TIM-3, and ICOS) with the ordered RECIST categories of tumor response. Logistic regression will be used to explore associations of the same tumor expressions and biomarkers with OR. Cox proportional-hazards (PH) regression will be utilized to evaluate the associations of these tumor expressions and biomarkers with PFS and OS.

The above analysis approaches will also be used to evaluate the effects of TBN and individual somatic mutations at baseline on RECIST response, OR, PFS, and OS. The effect on PFS and OS of TBN and individual somatic mutations that accumulate during treatment will be analyzed using either landmark analysis (25) or Cox regression with time-dependent covariates.

The sensitivity and specificity of NGS and CGP to assess MMR gene deficiency/MSI will be assessed using standard contingency-table methods with the gold standard being PCR-based DNA MSI-testing. Agreement between methods will also be assessed using Cohen's Kappa in conjunction with McNemar's test to test for systematic bias in the disagreements that occur.

The association of peripheral blood populations (absolute lymphocyte counts, number of T cells, T-cell subsets, NK cells, and B cells, as well as cellular phenotypes) with treatment and subject response will be explored using profile plots versus treatment cycle, in conjunction with longitudinal-analysis techniques such as mixed-models analysis or regression with generalized estimating equations to accommodate the non-independence among multiple measurements from the same subject over time.

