2.0 BACKGROUND & RATIONALE

2.1 Background

Endometrial cancer is the most common gynecologic malignancy with approximately 54,870 new cases and 10,170 estimated deaths related to the disease in the United States annually (1). Recently, using a comprehensive genetic investigation, The Cancer Genome Atlas (TCGA) Research Network provided compelling evidence that endometrial cancers result from heterogeneous somatic mutations and classified endometrial cancers into four categories: 1) polymerase epsilon (POLE)-ultramutated, 2) microsatellite instability hypermutated (MMR-defective), 3) copy-number low and 4) copy-number high, serous-like (2). In this landmark study, patients harboring POLE-ultramutated (7%) were found to have the best prognosis (Figure 1 Left panel below and reference #2). After the initial TCGA report, multiple studies from our group as well as others have confirmed that despite commonly being of high histological grade, ultra/hyper-mutation is correlated with a more favorable prognosis in both Type I and Type II endometrial cancer patients (3-6). Unfortunately, however, as recently demonstrated by the whole exome sequencing (WES) of 243 patients with endometrial disease enrolled in GOG86P (Figure 1 below, right panel, ref. # (7) and [name] MD personal communication) over 25% of patients developing recurrence, which was fatal in the majority of the cases, harbored an ultramutated or hypermutated tumor phenotype. Novel, effective treatment options for ultramutated and hypermutated recurrent endometrial cancer patients remain therefore desperately needed.

Figure 1. Molecular stratification of 232 WES endometrial cancer patients (TCGA report, left Panel, ref. #2) vs 243 endometrial cancer patients with recurrent disease sequenced using WES enrolled in GOG 86P (right panel, ref#7). In GOG86P patients with ultramutated and hypermutated tumors accounted for 2% and 24% of all recurrences, respectively.

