We will target an accrual of 12 eligible and evaluable patients in the first stage of the study, but permit the accrual to range from 8 to 15 for administration reasons. If there are more than 0 out of 8-13 or 1 out of 14-15 patients responding (complete or partial response) and medical judgment indicates, accrual to the second stage of the trial will be initiated. Otherwise, the study will be stopped and the treatment will be classified as clinically uninteresting. If the study advances to the second stage, then a cumulative accrual of 22 eligible and evaluable patients will be targeted, but permitted to range from 18 to 25 for administration reasons. If more than 1 out 18, or 2 out 19-25 patients respond and medical judgment indicates, then the study regimen will be considered worthy for further investigation.

Under the assumed accrual ranges of 8 to 15 (stage 1) and 18 to 25 (cumulatively after stage 2), and under the rejection rules associated with these accrual ranges, if the true probability of tumor response is 5%, then the study has a 65% average probability of early termination and an average 10% probability of incorrectly declaring the study regimen interesting; if the true probability of tumor response is 25%, then the study has a 90% average chance of correctly classifying the study regimen as being interesting.

Table 8: Accrual Ranges and Associated Rejection Rules.					
Stage of Accrual	Targeted Cumulative Accrual	Limits of Actual Accrual	Max Number of Responses to Reject Study Regimen		
1	12	8-15	0/(8-13), 1/14-15		
2	22	18-25	1/(18), 2/(19-25)		

The following table (Table 8) summarizes the accrual ranges and associated rejection rules.

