11.2 Definitions of Primary Endpoints and How These Will Be Analyzed

- 1) Proportion of objective tumor response as assessed by RECIST.
- 2) Frequency and severity of adverse events as assessed by CTCAE v4 and corresponding frequency table will be provided as descriptive statistics.

All patients who receive any therapy will be evaluated for both treatment efficacy and toxicity. Only those patients who are deemed "ineligible" or who receive no therapy will be eliminated from the analysis. While on occasion, circumstances may prevent the determination of treatment efficacy, such patients will be included in the analysis and labeled as "indeterminate." This category will be listed and be reflected in the calculation of the proportion responding.

11.3 Sample Size and Power Calculations:

The sample size and power calculations will be based on the optimal flexible two-stage method (24). This method assumes that the number of patients responding to the study regimen has binomial distribution and the accrual combination for stage 1 and 2 is uniformly distributed.

The minimum and maximum accruals for this study are 8 and 25 eligible and evaluable patients, respectively.

Under the assumed accrual ranges of 8 to 15 (stage 1) and 18 to 25 (cumulatively after stage 2), and under the rejection rules shown in **Table 8** for these accruals, the study has an average power of 90.0% at a target alpha=10% significance level to detect the 20% increase in the rate of tumor response from the null-hypothesis rate of 5% to a clinically interesting rate of 25% under the alternative hypothesis. The study's true alpha has an average of 9.5% with a 64.9% average probability of early termination and average expected sample size of 15.14 subjects under the null hypothesis.

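### For mutations carried by only one to three patients, the planned logistic regression against objective response will often have no finite odds ratio, and section 11.7 names no sparse-data method

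*Combined protocol and SAP*

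**What the plan says.** The first paragraph of section 11.7 deals with tumour expression of PD-L1 and PD-1, lymphocyte infiltration and other immune markers. For objective response (OR) it states: "Logistic regression will be used to explore associations of the same tumor expressions and biomarkers with OR". Plots and Spearman correlation are planned against ordered RECIST category, and Cox regression for PFS and OS.

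The paragraph that matters here is the second. It says the same approaches will be used to "evaluate the effects of TBN and individual somatic mutations at baseline on RECIST response, OR, PFS, and OS". Logistic regression of OR on single mutations is therefore planned explicitly.

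On sample size, section 11.3 states: "The minimum and maximum accruals for this study are 8 and 25 eligible and evaluable patients, respectively". On how rare the ultramutated group may be, the Figure 1 caption in section 2.1 states: "In GOG86P patients with ultramutated and hypermutated tumors accounted for 2% and 24% of all recurrences, respectively". The Figure 2 caption in the same section splits 65 MSI tumours into 52 with MLH1 promoter methylation and 13 with a mutation in an MMR gene.

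Section 11.7 does not say how the logistic model is estimated. It sets no minimum number of carriers and gives no exact, penalised or other fallback for sparse tables.

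**The concern.** A single mutation is a yes/no marker, and in 25 patients many mutations will have one, two or three carriers. If all carriers respond, or none does, one cell of the 2x2 table is empty and the maximum-likelihood odds ratio is infinite or zero. Software usually still prints a result: a very large coefficient, an enormous standard error and a Wald p-value near 1. A reader would take that as no association, although the same data may be the most suggestive pattern in the trial. The problem also grows with the strength of the association, so it is worst for the signals the analysis is looking for.

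Objective 1.3.1B asks how individual somatic mutations relate to response, and section 2.1 gives this as a reason for whole exome sequencing of every treated patient. The choice of estimator decides whether that question gets a usable answer for rare mutations.

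**Working it through.** **1. The plan's own design figures.** These fix the sample size and response rates used below. Section 11.3 gives "the study has an average power of 90.0% at a target alpha=10% significance level" for a change "from the null-hypothesis rate of 5% to a clinically interesting rate of 25% under the alternative hypothesis", and "true alpha has an average of 9.5% with a 64.9% average probability of early termination and average expected sample size of 15.14 subjects". I applied the Table 8 rules (continue with "more than 0 out of 8-13 or 1 out of 14-15 patients responding"; final cut-offs of 1 in 18 and 2 in 19-25) to the 8 x 8 = 64 equally likely accrual pairs, using exact binomial sums. Power is 90.05%, alpha 9.45%, early termination 64.9% and expected sample size 15.13. The stated figures reproduce to rounding.

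**2. Inputs.**
- N = 25 (maximum); 22 (cumulative target) as a check.
- Response rate 25% from the plan. 50% is my assumption, to show a range.
- POLE-like prevalence: 2/(2+24) = 7.7%, so 25 x 0.077 = 1.9 carriers expected. This assumes enrolment follows the Figure 1 mix.
- MMR-gene mutation prevalence: 13/65 = 20%, so 5 of 25. This assumes the Figure 2 mix carries over.

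**3. Fixed numbers of carriers and responders, no association.** With c carriers and r responders among n = 25, the probability that all carriers or no carriers respond is [C(n-r, c) + C(r, c)] / C(n, c). For r = 6:
- c = 1: (19 + 6)/25 = 100%
- c = 2: (171 + 15)/300 = 62%
- c = 3: (969 + 20)/2300 = 43%
- c = 5: (11628 + 6)/53130 = 22%

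With c = 2, the figure is 78% for 3 responders and 48% for 12.

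**4. Random numbers of carriers and responders.** With m carriers and response rate p in both groups, P(empty cell) = 1 - [1 - p^m - (1-p)^m] x [1 - p^(N-m) - (1-p)^(N-m)]. I averaged this over m ~ Binomial(N, prevalence) and counted m = 0 as no estimate.

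| Marker | N | 25% response | 50% response |
|---|---|---|---|
| POLE-like, 7.7% | 25 | 71% | 62% |
| POLE-like, 7.7% | 22 | 75% | 67% |
| MMR-gene mutation, 20% | 25 | 29% | 14% |
| MMR-gene mutation, 20% | 22 | 35% | 19% |

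The POLE-like rows include trials with no carrier at all: 13.5% at N = 25 and 17.2% at N = 22. Given at least one carrier, the N = 25 figures are 66% and 56%.

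**5. Effect of a real association.** Take illustrative response rates of 90% in carriers and 40% in others. With 2 carriers of 25, an empty cell occurs in 82% of datasets; with 5 carriers, in 59%.

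**6. What the output looks like.** Suppose 2 of 2 carriers and 4 of 23 non-carriers respond.
- Standard fit: when the iterations stop, the log-odds ratio is near 22, its standard error about 12,500 and the Wald p-value above 0.99.
- Fisher's exact test: C(6,2)/C(25,2) = 15/300 = 0.050. The other two possible tables are more probable, so this is also the two-sided value.
- Firth estimate (here the same as adding 0.5 to each cell): (2.5 x 19.5)/(0.5 x 4.5) = 21.7. The standard error of the log-odds ratio is sqrt(1/2.5 + 1/0.5 + 1/4.5 + 1/19.5) = 1.64, giving a Wald-type 95% interval of 0.88 to 534.

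**7. Where the problem is small.** For a continuous marker with no association, complete separation has probability 2/C(N, r) for r responders. Averaged over r at N = 25 and 25% response, and counting r = 0 or N as failure, that is about 0.15%. For a Cox model with 2 carriers of 25, no association and all events observed, an infinite estimate needs both carriers to fail first or both last: 2/300, under 1%. If only the first 12 events are observed, it is (C(13,2) + 1)/300 = 79/300 = 26%, against 48% for the logistic model with 12 responders.

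**The case against.** The strongest reply is that the plan never says maximum likelihood. Firth and exact logistic regression are both logistic regression, so the analyst could use them without departing from the plan. That is fair as to wording. But unqualified logistic regression is ordinarily read, and run, as maximum likelihood with Wald output. A likelihood-ratio test from the same fit would not collapse in this way, but the section does not ask for one. Leaving the choice until non-convergence is seen is what a plan should avoid.

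The second reply is that the analyses are exploratory and the plots and Spearman correlations survive an empty cell. Both are true. They limit the damage, but they do not supply the odds ratio that 11.7 promises.

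Third, better methods add little information. The interval of 0.88 to 534 shows this, and with no carriers nothing can be estimated. This stands: the gain is an honest, finite statement of uncertainty in place of a misleading one.

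A reader might go further and infer that the mutation analyses fail in the subgroups of most interest, or that Cox regression and the immune markers are equally affected. The documents do not support that. The sentence on logistic regression for immune markers concerns measures that are mostly graded or continuous. Mutation burden is a count. The MMR-gene contrast is estimable in about 65% to 86% of datasets without association (fewer if the effect is strong), and Cox separation is less frequent. A reader might also count markers times outcomes and predict a number of false positives. Section 11.7 sets no significance level for these associations, so such a count would bring in a threshold the plan does not use.

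**Conclusion.** The point holds for rare binary mutations analysed against OR, and only there. With one to three carriers among 25 patients and 6 responders, ordinary logistic regression has no finite odds ratio in 43% to 100% of datasets without association. For a POLE-like marker the overall figure is about 62% to 71% at N = 25. In those datasets the default Wald p-value reads as no association whatever the data show.

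The carrier counts assume that enrolment resembles the mixes in section 2.1. Eligibility by NGS or by standard MSI and IHC testing (section 3.2.3) could shift them. The 50% response rate and the strong-association rates are illustrative. The primary endpoint, sample size and two-stage decision rule are unaffected. This is a cheap improvement to an exploratory analysis, not a flaw in the trial's main conclusion.

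**What to change.** In section 11.7, for binary mutation markers against OR, replace unqualified logistic regression with one of two named methods: Firth-penalised logistic regression with profile-likelihood intervals, or exact logistic regression or Fisher's exact test. Fit one marker per model. For PFS and OS, use Firth-penalised Cox regression where the ordinary Cox estimate is not finite. Report every mutation tested, including those with an empty cell. For very rare mutations, give response counts with exact intervals, using a minimum carrier count fixed in advance.

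The cost is a few sentences in the plan, a different software option and a little more analysis work. Penalised estimates are shrunk slightly toward no effect, and intervals for rare mutations will be very wide. No change to design or sample size is needed.
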